5.3.3. Analysis Methods

5.3.3.1. Main Estimator (Analysis) for the Primary Estimand

A MMRM will be used to determine the change from baseline in Cardiovascular measurement at Week 32 or Week 16 in the open label phase to compare the participant groups of nicotine users vs non-nicotine users, will be analyzed using a MMRM based on observed case data. The models will include baseline CFR measurement at Week 0, Baseline before first administration of guselkumab as a covariate, and Nicotine use, BMI, presence or absence of PsA, age, gender, and visit.

The estimates for the primary estimand of the treatment effect of guselkumab will be provided by the difference of change from baseline at Week 32 in the LSmeans. The 95% CI for the differences in LSmeans and p-values will be calculated based on the MMRM. The within-subject covariance between visits will be estimated via an unstructured variance-covariance matrix. In case of convergence problems, alternative variance-covariance structures will be tried in the following order, with the first structure that converges being used in the analysis: heterogeneous Toeplitz, standard Toeplitz, and autoregressive order 1 (AR[1]) with separate subject random effect.

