#### OVERALL DESIGN

This is an interventional, single-arm, open-label, oligocentric study to evaluate the effect of guselkumab on cardiovascular risk surrogate markers in adult men and women diagnosed with moderate-to-severe plaque psoriasis (with or without PsA) for at least 6 months prior to study entry. Eligibility of the participants will be assessed at 2 screening visits; at Screening Visit S1, participants will be screened at the dermatology department based on skin assessments, medical history, and laboratory parameters. Participants fulfilling eligibility criteria at Screening Visit S1 will be referred to the cardiology department, and will undergo cardiologic assessments (GLS, CFR [via transthoracic doppler echocardiography] and cfPWV) at Screening Visit S2, and again at Week 0. Only participants with CFR ≥2 and ≤3.5 at both these time-points will be enrolled in the study. The CFR measurement at Week 0 will be considered as the baseline value.

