#### 9. STATISTICAL CONSIDERATIONS

Statistical analysis will be done by the Sponsor or under the authority of the Sponsor. A general description of the statistical methods to be used to analyze the efficacy and safety data is outlined below. Specific details will be provided in the Statistical Analysis Plan.

Descriptive statistics, such as mean, standard deviation (SD), median, inter quartile range, minimum, and maximum for continuous variables, and counts and percentages for discrete variables will be used to summarize most data. In addition, graphical data displays (eg, line plots) and participant listings may also be used to summarize/present the data.

In general, for continuous or ordinal efficacy endpoints, a Mixed-Effect Model Repeated Measures (MMRM) model will be used. Covariates such as BMI, smoking status, presence, or absence of PsA, age, gender, left ventricular mass index and hypertension diagnosis will be incorporated into these models. For binary efficacy endpoints, 95% confidence intervals for binomial proportions will be provided using exact methods, such as Clopper-Pearson or Chan-Zhang.

In general, all statistical tests will be performed at a 2-sided significance level of  $\alpha$  0.05.

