3. SAMPLE SIZE DETERMINATION

The initial sample size calculation was based on the assumption that participants will show an average increase of 20% in CFR at Week 32. To detect a CFR, mean change of 0.3 from baseline with 80% power, and assuming a standard deviation of 0.8 and a 5% dropout rate, 50 participants are expected to be enrolled in the study. Sample size may be increased if the dropout rate is higher than expected, in accordance with the sample size assumptions stated above.

After the decision to prematurely terminate the study, this sample size calculation was no longer relevant.

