5. STATISTICAL ANALYSES

5.1. General Considerations

Descriptive statistics (eg, mean, median, standard deviation (SD), minimum, and maximum) will be used to summarize continuous variables. Counts and percentages will be used to summarize categorical variables. Graphic data displays may also be used to summarize the data. In addition, graphical data displays (eg, line plots) and participant listings may also be used to summarize the data.

The summarized data will be presented by Nicotine-user, non-Nicotine user and total group.

Baseline Value: For all endpoints the last non-missing measurement prior to or on the day of the first administration of the study treatment (guselkumab) will be the Baseline value in the study (i.e., at 'Week 0, Baseline' analysis visit, following assignment of the actual visits using visit windows, as indicated in Table 2).

Level of Significance: In general, all tests will be performed at a 2-sided significance level of 0.05, unless otherwise specified. All interval estimations will be reported using 2-sided 95%CI. Nominal p-values will be presented.

Change from Baseline:

For the continuous variables pertaining to the cardiology outcomes, skin related outcomes, or paper PRO outcomes the determination of change from baseline will be determined only when both, baseline and the measurement for the particular visit is available.

Change from Baseline at visit x = Measurement from the visit x - Baseline value of the parmeter

The number of patients with missing change from baseline values will be also presented in the statistical outputs.

For continuous or ordinal efficacy endpoints, a Mixed-effect Model for Repeated Measures (MMRM) will be used. Covariates such as Nicotine use, body mass index (BMI), presence, or absence of PsA, age, gender, and visit will be incorporated into these models.

For binary efficacy endpoints, 95% confidence interval [CI] for binomial proportions will be provided using exact methods, such as Clopper-Pearson or Chan-Zhang.

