5.3.2. Estimand

Primary Trial Objective: To evaluate the effect of guselkumab on CFR measured by transthoracic doppler-echocardiography, in participants with moderate-to-severe psoriasis and intermediate cardiovascular risk. Intermediate cardiovascular risk is defined by CFR ≥ 2 and ≤ 3.5 at Screening Visit S2.

Estimand Scientific Question of Interest: What level of change from baseline of CFR considered to have benefited from guselkumab for the pre-specified duration (32 weeks).

Study intervention:

• Guselkumab (100 mg SC [Subcutaneous] injections at Week 0, 4, 12, 20 and 28)

Population: Participants with moderate to severe plaque psoriasis (with or without PsA) for at least 6 months prior to study entry. The target population consists of men or women aged 18 years and above with moderate to severe plaque psoriasis of at least 6 months' duration, defined as psoriasis area and severity index (PASI) \geq 12, and involved body surface area (BSA) \geq 10% at Screening Visit S1 and CFR with \geq 2 to \leq 3.5 at Screening Visit S2. Participants should not be with CFR of \leq 2 or \geq 3.5 at both Screening Visit S2 and Week 0.

Variable: Change from baseline in the CFR measurement at Final Efficacy Visit (Week 32). The CFR measurement at Week 0, Baseline will be considered as baseline value. Participants who had adequate primary endpoint measurements will be assessed at Final Efficacy Visit (Week 32) considering as observed for the analysis.

Summary measure (Population-level summary): Least squares means (LSmeans), together with the 95% CI and p-values based on the MMRM.

Intercurrent events and their corresponding strategies:

Intercurrent Events	Strategy for Addressing Intercurrent Events and Its Description
	Composite Strategy: A participant with this intercurrent event will be excluded from the analysis.

^{*} List of concomitant medications from ADaM datasets will be shared with the clinical team after the receipt of SDTM data by the programming team for each data cut. The clinical team will review the list and flag the appropriate disallowed medications. This list will be used for the intercurrent events.

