5.4.1.3 Analysis Methods

Main Estimator (Analysis) for the Primary Estimand

A MMRM will be used to determine the change from baseline in Cardiovascular measurement at Week 16 or Week 32 in the open label phase to compare the participant groups of nicotine users vs non-nicotine users, will be analyzed using a MMRM based on observed case data. The models will include baseline CFR/GLS/cf-PWV measurement at Week 0, Baseline before first administration of guselkumab as a covariate, and Nicotine use, BMI, presence, or absence of PsA, age, gender, and visit.

The estimates for the primary estimand of the treatment effect of guselkumab will be provided by the difference of change from baseline at Week 32 in the LSmeans. The 95% CI for the differences in LSmeans and p-values will be calculated based on the MMRM. The within-subject covariance between visits will be estimated via an unstructured variance-covariance matrix. In case of convergence problems, alternative variance-covariance structures will be tried in the following order, with the first structure that converges being used in the analysis: heterogeneous Toeplitz, standard Toeplitz, and AR(1) with separate subject random effect.

5.5. Tertiary/Exploratory Endpoint(s) Analysis:

As the study was prematurely terminated all exploratory endpoints will be presented by listing only with change from baseline where applicable.

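### The single-arm LSmean of change is tested against zero with a baseline-adjusted model whose usual standard error is too small whenever change depends on baseline

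*SAP*

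**What the plan says.** The hypothesis in SAP 2 concerns one arm: the change from baseline in CFR at Week 32 is positive. The population-level summary in SAP 5.3.2 is "Least squares means (LSmeans), together with the 95% CI and p-values based on the MMRM". The estimator in SAP 5.3.3.1 adds nicotine use, BMI, PsA, age, gender and visit to the baseline term: "The models will include baseline CFR measurement at Week 0, Baseline before first administration of guselkumab as a covariate". SAP 5.4.1.2 and 5.4.1.3 repeat this for the secondary endpoints: "The models will include baseline CFR/GLS/cf-PWV measurement at Week 0, Baseline before first administration of guselkumab as a covariate".

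The level is set in SAP 5.1: "In general, all tests will be performed at a 2-sided significance level of 0.05, unless otherwise specified". Intervals are two-sided 95% and p-values are called nominal. Protocol 9 also uses a two-sided 0.05.

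SAP 5.3.3.1 and 5.4.1.3 describe the model as comparing nicotine users with non-users, and they attach the CI and p-value to differences in LSmeans. No section states the covariate values at which LSmeans are taken, the standard error or degrees-of-freedom method, or whether inference is conditional on the observed baselines.

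**The concern.** The hypothesis and the estimand call for one number, the overall mean change, with an interval for the target population. Adjusting for baseline removes from the residual the part of the change that baseline explains. The default standard error is built from that residual alone. A between-group difference loses nothing by this, because the common baseline mean cancels. A single-arm mean does lose something: another sample would have another mean baseline, and hence another mean change, and the standard error ignores that.

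At stake are the coverage of the intervals labelled 95% for CFR, GLS and cfPWV, and the level of the test that the change is positive.

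**Working it through.** **Inputs**

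| Input | Value | Source |
|---|---|---|
| Level | 0.05, two-sided | SAP 5.1; Protocol 9 |
| SD | 0.8, read here as the SD of the change | SAP 3 |
| n | 50 × 0.95 = 47.5, so 47 | SAP 3; final n not given |
| Baseline CFR SD | 1.5/√12 = 0.433 for a uniform spread over 2 to 3.5; 0.30 and 0.36 also tried | Assumption; range from Protocol 1.1 |
| Slope of change on baseline, b | 0 to -1 | Assumption |
| Baseline/follow-up correlation, ρ (GLS, cfPWV) | 0.3 to 0.85, equal variances | Assumption |

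The CFR range comes from the entry rule: "Only participants with CFR ≥2 and ≤3.5 at both these time-points will be enrolled in the study".

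**The plan's own figure.** The plan gives no figure for this standard error or for actual type I error. Its sample size rests on a "mean change of 0.3 from baseline with 80% power" and continues "assuming a standard deviation of 0.8 and a 5% dropout rate, 50 participants are expected to be enrolled in the study". The two-sided formula gives (0.8 × (1.96 + 0.842)/0.3)² = 55.8, so 56 evaluable and 56/0.95 = 59 enrolled. The stated 50 does not reproduce at that level; a one-sided 0.05 t-test gives 46 evaluable and 49 enrolled. That is a separate matter. Only the SD of 0.8 and n of 47 are carried forward.

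**Formula.** Take the LSmean at the sample-mean baseline, with s² the residual variance:

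- usual model variance = s²/n
- variance for the population mean change = (s² + b²·Var(baseline))/n = Var(change)/n
- ratio of model SE to true SE = √(1 - R²), where R² = b²·Var(baseline)/Var(change)
- actual type I error = 2 × (1 - Φ(1.96 × √(1 - R²)))

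The ratio does not depend on n.

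**CFR.** Example at b = -0.7: R² = 0.49 × 0.1875/0.64 = 0.144, the ratio is 0.925, and 1.96 × 0.925 = 1.81, which gives 7.0%. At n = 47 the true SE is 0.8/√47 = 0.117 and the model SE is 0.108.

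| Slope | SE ratio (SD 0.433) | Type I, SD 0.30 | SD 0.36 | SD 0.433 |
|---|---|---|---|---|
| 0 | 1.000 | 5.0% | 5.0% | 5.0% |
| -0.3 | 0.987 | 5.2% | 5.2% | 5.3% |
| -0.5 | 0.963 | 5.4% | 5.6% | 5.9% |
| -0.7 | 0.925 | 5.9% | 6.3% | 7.0% |
| -1.0 | 0.841 | 6.9% | 8.0% | 9.9% |

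**Simulation for CFR.** The single-visit model with all SAP covariates was run at observed margins, n = 47, baseline SD 0.433, 10,000 runs per setting. For the five slopes it gave 5.0%, 5.0%, 5.5%, 6.5% and 9.8%. A two-visit unstructured MMRM (4,000 runs) gave 4.8%, 5.5%, 6.4% and 9.1% at slopes 0, -0.5, -0.7 and -1.0. A one-sample t-test on the changes stayed at 4.5-5.4% for n = 12, 20 and 47.

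**GLS and cfPWV.** These have no entry range. With equal variances, b = ρ - 1 and the SE ratio is √((1 + ρ)/2).

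| ρ | SE ratio | Type I (formula) | Simulated, n = 47 |
|---|---|---|---|
| 0.85 | 0.962 | 5.9% | 5.7% (all covariates) |
| 0.7 | 0.922 | 7.1% | 7.0% |
| 0.5 | 0.866 | 9.0% | 8.8% |
| 0.3 | 0.806 | 11.4% | 10.9% |

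**Contrasts that behave differently**

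- Nicotine-group difference in LSmeans: 4.9-5.3% at every slope (single-visit covariate model, n = 47).
- LSmeans at equal class margins, n = 47: about 5% at slope -0.5 and 8.2% at -1.0.
- Baseline dropped but BMI kept, with BMI assumed to explain 20% or 30% of the variance of change: 7.9% and 9.7% at n = 47.

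**The case against.** The strongest reply is that the SAP never commits to this standard error. SAP 5.3.3.1 and 5.4.1.3 put the CI and p-value on differences in LSmeans between nicotine groups, where the baseline mean cancels. That is right for that contrast. It does not dispose of the point, because a nicotine-group difference cannot show whether the change is positive. The estimand section asks for the LSmeans themselves with CI and p-value from the MMRM, and no other standard error is named.

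Second, treating covariates as fixed is ordinary regression practice, and the interval is valid conditional on the observed baselines. That is true, but SAP 5.3.2 labels the measure a population-level summary for a defined target population.

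Third, the size depends on quantities that the documents do not give. This stands. The formula gives 6.3% at a correlation of 0.8 and 5.6% at 0.9. The requirement for the same lab, machine and software at every visit (Schedule of Activities footnote g; Protocol 8.1) makes a high correlation plausible. A negative CFR slope is also plausible, since baseline carries measurement error and is range-limited, but its size is unknown.

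Fourth, the trial stopped early and p-values are nominal, so no confirmatory error control is claimed. This lowers the stakes of the test. It does not excuse under-coverage of intervals labelled 95%.

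**Conclusion.** The point holds in a conditional form. If the single-arm LSmean of change is read as the population mean change, and the default model-based standard error is used, the 95% CI is too narrow and the test against zero exceeds 5% whenever change depends on baseline. For CFR the excess is nil at slope 0, within about 1 point up to slope -0.5, about 2 points at -0.7 and about 5 points at -1.0. For GLS and cfPWV it is about 1 point at correlation 0.85, 2 at 0.7, 4 at 0.5 and 6 at 0.3. These figures assume an SD of change of 0.8 and a baseline SD of 0.433 for CFR, and equal variances for the other two.

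A reader might infer that every interval in the plan is too narrow, or that type I error certainly exceeds 5%. The documents do not support either reading: the nicotine-group difference is unaffected, the SAP does not specify the standard error, and no slope or correlation is given. Nor is baseline the only source. Any covariate that predicts change has the same effect on a single-arm LSmean.

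**What to change.** In SAP 5.3.3.1 and 5.4.1.3, state that the overall mean change at Week 32 (and Week 16), tested against zero, is the contrast for the hypothesis in SAP 2. Then use one of the following for CFR, GLS and cfPWV:

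- an MMRM with the Week 0, 16 and 32 values as responses and the covariates as main effects only, reporting LSmean(Week 32) minus LSmean(Week 0), and likewise for Week 16. With main effects only, the covariate terms cancel from the contrast;
- the unadjusted one-sample (paired) change with its t-interval.

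Do not simply delete the baseline covariate, since the remaining covariates cause the same problem if they predict change. Keep the baseline-adjusted model for the nicotine-group difference. State the LSmean margins and the degrees-of-freedom method.

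The cost is SAP wording and one model statement, with no new data. For CFR at baseline SD 0.433, intervals widen by the reciprocal of the SE ratio: 1/0.963 = 1.04 at slope -0.5, 1/0.925 = 1.08 at -0.7 and 1/0.841 = 1.19 at -1.0. That is the width needed for the stated coverage.

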2. STATISTICAL HYPOTHESES

The primary hypothesis of this study is that guselkumab (administered as 100 mg at Weeks 0, 4, 12, 20 and 28) is effective in reducing surrogate markers of cardiovascular risk as assessed by the change from baseline of CFR measurement at Week 32 (i.e., change from baseline of CFR measurement at Week 32 is positive).

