5.4. Secondary Endpoint(s) Analysis

5.4.1. Key Confirmatory Secondary Endpoint(s)

The key secondary endpoints include the following at Week 16 and Week 32:

- Change from baseline in CFR at Week 16
- Change from baseline in absolute GLS at Week 16 and Week 32.
- Change from baseline in carotid-femoral pulse wave velocity (cfPWV) at Week 16.
- Change from baseline in cfPWV at Week 32.
- Change from baseline in CFR at Week 16 and Week 32 among participants with CFR in the ranges of 2 to >2.75 and ≤ 2.75 to 3.5 at baseline.
- Change from baseline in CFR at Week 16 and Week 32 among nicotine users and non-users.
- Change from baseline in absolute GLS at Week 16 and Week 32 among nicotine users and non-users.
- Change from baseline in cfPWV at Week 16 and Week 32 in nicotine users and nonusers.
- Rate of Adverse Events (AEs) among participants treated with guselkumab at Week 16 and Week 32.

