5.4.1.2 Estimand

Secondary Trial Objective: To evaluate the effect of guselkumab on CFR/GLS/cf-PWV measured by transthoracic doppler-echocardiography, in participants with moderate-to-severe psoriasis and intermediate cardiovascular risk. Intermediate cardiovascular risk is defined by CFR ≥ 2 and ≤ 3.5 at Screening Visit S2.

Estimand Scientific Question of Interest: What level of change from baseline of CFR/GLS/cf-PWV considered to have benefited from guselkumab for the pre-specified duration (16 weeks).

Study intervention:

• Guselkumab (100 mg SC [Subcutaneous] injections at Week 0, 4, 12, 20 and 28)

Population: Participants with moderate to severe plaque psoriasis (with or without PsA) for at least 6 months prior to study entry. The target population consists of men or women aged 18 years and above with moderate to severe plaque psoriasis of at least 6 months' duration, defined as PASI \geq 12, and involved BSA \geq 10% at Screening Visit S1 and CFR with \geq 2 to \leq 3.5 at Screening Visit S2. Participants should not be with CFR of \leq 0 r \geq 3.5 at both Screening Visit S2 and Week 0.

Variable: Change from baseline in the CFR measurement at Week 16. The CFR measurement at Week 0, Baseline will be considered as baseline value. Similarly, for other secondary endpoints of GLS/cf-PWV at Week 16 and Week 32. Participants who had adequate secondary endpoint measurements will be assessed at Week 16 as per Table 2 and Final Efficacy Visit (Week 32) considering as observed for the analysis.

Secondary Estimand:

Summary measure (Population-level summary): LSmeans, together with the 95% CI and p-values based on the MMRM.

Intercurrent events and their corresponding strategies:

Intercurrent Events	Strategy for Addressing Intercurrent Events and Its Description
	Composite Strategy: A participant with this intercurrent event will be excluded from the analysis.

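### SAP 5.3.3.1 takes the guselkumab effect from a difference in LSmeans in a model set up to compare nicotine users with non-users, not from the overall Week 32 change

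*SAP*

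**What the plan says.** SAP 1.2 describes a single-arm, open-label study. SAP section 2 spells out the primary hypothesis: "change from baseline of CFR measurement at Week 32 is positive". SAP 5.3.2 gives the population-level summary as "Least squares means (LSmeans), together with the 95% CI and p-values based on the MMRM", with no contrast and no null value.

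SAP 5.3.3.1 turns this into an estimator. The MMRM is used "in the open label phase to compare the participant groups of nicotine users vs non-nicotine users". The "treatment effect of guselkumab will be provided by the difference of change from baseline at Week 32 in the LSmeans", and "The 95% CI for the differences in LSmeans and p-values will be calculated based on the MMRM". The listed terms are baseline CFR, nicotine use, BMI, PsA, age, gender and visit.

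SAP 5.4.1.3 repeats this text for the secondary endpoints, including the purpose "to compare the participant groups of nicotine users vs non-nicotine users". It carries a heading for the primary estimand and gives the estimate at Week 32 only, although SAP 5.4.1.2 frames the secondary question at 16 weeks. Nicotine status already has its own secondary endpoints in SAP 5.4.1, for example "Change from baseline in CFR at Week 16 and Week 32 among nicotine users and non-users", and is the subgroup defined in SAP 5.7.8.

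**The concern.** With one arm and no comparator, the quantity that bears on section 2 is the mean change at Week 32, set against 0. Section 5.3.3.1 does not name it. It names a comparison of two non-randomised subgroups and then labels a difference in LSmeans as the guselkumab effect.

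If the section is programmed as written, two errors can follow. A real rise in CFR common to users and non-users would not show in the reported effect or its p-value. A difference related to nicotine use, which is not caused by the drug, could be reported as a guselkumab effect.

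**Working it through.** **What each section targets.** Let μU and μN be the mean Week 32 changes in users and non-users.

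| Place | Quantity |
|---|---|
| SAP 2 | overall mean change, above 0 |
| SAP 3 | overall mean change of 0.3, SD 0.8 |
| SAP 5.3.2 | LSmeans; no contrast, no null value |
| SAP 5.3.3.1 | a difference in LSmeans; only grouping named is users v non-users |

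SAP 5.1 already defines the response as visit value minus baseline. A difference of change from baseline is therefore a second subtraction, and the plural differences in LSmeans is contrast wording. On that reading the estimate is μU − μN. If both equal δ, then δ − δ = 0 whatever the size of δ.

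**The plan's own figure.** Inputs from SAP 3: change 0.3, SD 0.8, 80% power, 5% dropout, 50 enrolled. One-sample normal formula: n = (SD × (zα + zβ) / change)².

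- Two-sided 5%: (0.8 × (1.960 + 0.842) / 0.3)² = 55.8, so 56 evaluable; 56 / 0.95 gives 59 enrolled. With the t-test, 58 evaluable and 62 enrolled.
- One-sided 5%, t-test: 46 evaluable; 46 / 0.95 gives 49 enrolled, close to 50.

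So 50 is roughly a one-sample size, and only one-sided. The sidedness is a separate matter. What counts here is that 50 was not sized for a group contrast: detecting a 0.3 difference between groups (SD 0.8, two-sided 5%, 80% power) needs 112 per group at 1:1, or 94 + 141 at 2:3.

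**Precision.** Planned groups in SAP Figure 1: 20 users, 30 non-users.

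- SE of the overall mean: 0.8 / √50 = 0.113.
- SE of the difference: 0.8 × √(1/20 + 1/30) = 0.231.
- Ratio: √(1 / (0.4 × 0.6)) = 2.04, the same at any N with this split.

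**Rejection rates when everyone changes by 0.3** (SD 0.8, two-sided 5%, unadjusted t-tests):

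| Evaluable N | Overall change v 0 | User v non-user contrast |
|---|---|---|
| 47 (50 less 5%) | 71% | 5% |
| 30 | 51% | 5% |
| 20 | 36% | 5% |
| 10 | 19% | 5% |

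Simulation agrees. In 40,000 trials each, the contrast rejected in 5.0% (4 v 6), 5.1% (8 v 12) and 4.9% (19 v 28), while the one-sample test on the same data rejected in 18%, 36% and 71%. With 20 v 30 over 20,000 trials, the contrast averaged 0.00 and the overall change 0.30.

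**The case against.** The sentence about the difference names no groups. It also speaks of a guselkumab effect at Week 32. The listed model has no nicotine-by-visit term, so a user/non-user contrast from it would be identical at both visits, and only a visit LSmean would be specific to Week 32. A lenient reader can therefore take the difference to be the Week 32 LSmean change itself. That argument has weight and shows that the text is ambiguous. It does not remove the problem: on either reading the section states neither the overall LSmean as the estimate nor a test against 0, and nicotine use remains the only comparison it names.

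Section 5.3.2 is less specific than 5.3.3.1 and does not contradict it outright; the sharper conflict is with section 2. SAP 5.1 promises summaries for the total group, so a common rise would be visible descriptively, but that gives no model-based estimate or test. P-values are nominal, and programming instructions sit in the separate Data Presentation Specifications, so actual outputs may be sensible. SAP 6.2, which lists changes from the protocol, does not mention making a nicotine contrast the primary effect, and protocol section 9 uses smoking status only as a covariate.

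On the numbers, the 5% is simply the test's size. It shows that the two questions differ; it does not measure harm. The powers ignore covariate adjustment. Weighting users and non-users equally in the overall mean changes the SE ratio from 2.04 to 2.00, which is immaterial.

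**Conclusion.** The concern holds. As written, SAP 5.3.3.1 attaches the guselkumab effect and its p-value to a difference in LSmeans in a model whose stated purpose is a nicotine comparison, and no section names the overall Week 32 LSmean tested against 0. A shared effect of any size has expectation 0 in the nicotine contrast. That result does not depend on N.

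The SE ratio assumes the planned 40/60 split. The powers are illustrative only: they use the planning change and SD, the final N and split are not given, and SAP 3 sets the sample size calculation aside after early termination. Early stopping and nominal p-values lower the inferential stakes, but this is the primary estimator of the final analysis and must be corrected. The corrected estimate would still be an uncontrolled before-after change.

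**What to change.** - **SAP 5.3.3.1:** state that the primary estimate is the overall LSmean change from baseline in CFR at Week 32 in the FAS, with 95% CI and a two-sided test against 0. Say how the LSmean weights the levels of nicotine use, PsA and gender (equal or observed proportions), since the choice changes the estimate in a small unbalanced sample.
- **SAP 5.3.2:** add the null value of 0.
- **SAP 5.4.1.3:** correct the heading, and specify the same form of estimate for CFR at Week 16 and for GLS and cfPWV at Weeks 16 and 32.
- **Nicotine contrast:** report user and non-user LSmeans and their difference only under the existing secondary nicotine endpoints. Without a nicotine-by-visit term the model gives one common difference for both visits; add that term for the nicotine analysis only, and only if the available N supports it.

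The cost is wording in three sections and one estimate statement in the program. The primary analysis needs no new data and no new model.
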